Acute Pain group participants will be visited by study staff after their transfer to a floor unit (either normal care or step down; that is, after post-anesthesia care). Upon confirming their willingness participate, they will be randomized to receive either green, blue or clear glasses. Participants will be asked to wear their study glasses for at least 4 hours per day throughout their hospital stay and will be provided log books in which to record their glasses-wearing duration each day and any commentary they wish to share. During this visit, participants will also complete the PROMIS-57 Profile. The Patient-Reported Outcomes Measurement Information System (PROMIS) is a collection of patient-reported measures developed by an initiative of the National Institutes of Health as high-quality, well-validated, and standardized patient-reported outcomes measures across multiple domains. The PROMIS-57 Profile is a detailed, standardized battery of PROMIS measures covering anxiety, depression, fatigue, pain intensity, pain interference, physical function, sleep disturbance, and ability to participate in social roles and activities. On day of discharge or at 48 hours postoperative, whichever comes first, study

staff will again visit participants to collect the study glasses. Participants will again complete the PROMIS-57 Profile. During participants' inpatient stays, study staff will continue to coordinate with the primary care teams to monitor for any issues arising from the study or the use of the study glasses. Providers will be supplied with contact information to provide any feedback they wish to share.

For the postoperative patients in the study who are inpatient for the duration of the study, this is evaluated for them throughout their inpatient stay and the primary teams have the ability to address any sleep disturbance, mood change or change in the patients pain control per standard care. Should the providers caring for the patient or the patient themselves perceive the study intervention to be a significant contributor to the patients worsening condition, an adverse event will be recorded per the Data Safety Monitoring Plan and the patient will be withdrawn from the intervention/study.

Trial Procedures – Chronic Pain group:

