Chronic Pain group participants will begin study procedures immediately following their enrollment. Participants will be randomized to receive either green, blue or clear glasses and will complete the PROMIS-57 Profile. Participants will be asked to wear their study glasses for at least 4 hours per day for a period of 2 weeks. Unlike the Acute Pain group in which pain will typically self-resolve with operative healing and the hospital stay provides a convenient and applicable treatment timeline, the appropriate duration of green light therapy for use in chronic pain states is unknown. Preclinical findings suggest the onset of analgesic effects after 3 days. However, such timelines rarely translate directly to human populations. Most pharmacological analgesics achieve effect onset within minutes to hours, although the analgesic effects of antidepressants upon chronic pain states (which may also involve modulation of descending pain control mechanisms) can require a week or longer to manifest. Here, we have chosen a moderate 2-week duration to allow for a range of times-to-onset. Participants will be provided log books in which to record their glasses-wearing duration, average pain, and opioid use each day. They will also be invited to include any commentary they wish to share.

For outpatients with fibromyalgia who are enrolled for 2 weeks all patients are administered the PROMIS-57 profile which evaluates the domains of sleep, mood and pain at enrollment, week 1 and at week 2 when the intervention ends. If there is any worsening of the patients condition in any of the domains, they will be offered immediate evaluation and management for the same. Should the providers caring for the patient or the patient themselves perceive the study intervention to be a significant contributor to the patients worsening condition, an adverse event will be recorded per the Data Safety Monitoring Plan and the patient will be withdrawn from the intervention/study.

All patients are provided with a phone number to call should they suffer from any side effects or worsening of their condition including any sleep disturbances.

Participants in this group will be asked to complete the PROMIS-57 Profile at the 1-week and 2-week time points. Two copies of the PROMIS-57 questionnaire will be given to the patient for completion at week 1 and week 2. A member of the study staff will call the patients at week 1 to

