We calculate that a total enrollment of 120 participants will be sufficient to provide greater than 95% confidence in detecting issues with a 5% probability of occurrence. Divided evenly across Acute Pain and Chronic Pain groups (60 each) this sample will also provide approximately 80% confidence in detecting issues with a 5% probability of occurrence in only one group. This yields a 15 participant per condition (acute/chronic x green/clear/blue) sample size. Adding the blue glasses group to compare, continues to allow us a similar confidence in detecting issues with a 5% probability of occurrence in detecting issues with a 5% probability of occurrence in detecting issues with a 5% probability of occurrence in detecting issues with a 5% probability of occurrence in detecting issues with a 5% probability of occurrence in detecting issues with a 5% probability of occurrence in detecting issues with a 5% probability of occurrence in detecting issues with a 5% probability of occurrence in detecting issues with a 5% probability of occurrence in detecting issues with a 5% probability of occurrence in detecting issues with a 5% probability of occurrence in detecting issues with a 5% probability of occurrence in detecting issues with a 5% probability of occurrence in one group.

Interestingly, this chosen sample size also fulfills several other methods/guidelines for pilot trial sample sizes which range from 10 to 15 per condition. These methods have generally sought to power pilot trials to produce usable estimates of outcome measure values. While the appropriateness of such an approach is debated, it does suggest that our chosen sample size will be satisfactory to produce such estimates.

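### The stated adverse-event trigger requires someone who can see the lens colour to blame the glasses, so recorded counts depend on attribution and may differ between arms for that reason alone

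*Combined protocol and SAP*

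**What the plan says.** The same rule appears under Trial Procedures – Acute Pain group and Trial Procedures – Chronic Pain group. If the treating providers or the patient "perceive the study intervention to be a significant contributor to the patients worsening condition, an adverse event will be recorded". The full consequence is that "an adverse event will be recorded per the Data Safety Monitoring Plan and the patient will be withdrawn from the intervention/study". That monitoring plan is not part of the supplied text.

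Worsening that nobody ascribes to the glasses is treated differently. In the acute section the primary team deals with changes in sleep, mood or pain as usual care. In the chronic section, worsening in a PROMIS-57 domain leads to an offer of evaluation. Neither sentence calls for an event record.

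Other routes also collect information:

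- **PROMIS-57, all arms.** Acute: at the first floor visit, then at discharge or 48 hours. Chronic: at enrollment, week 1 and week 2.
- **Phone line.** Open for side effects or any worsening, with no attribution condition (chronic section and Study Interventions).
- **Log-book comments and provider feedback.** Collected in both groups.
- **Staff monitoring with the care teams (acute).** Directed at problems arising from the study or the glasses, so again tied to cause.

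The arms are clear (control), green and blue. The Eyeglasses section says the green pair was screened for having a matching clear version. No masking is described.

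Data Analysis and Statistical Considerations justifies 120 participants as "sufficient to provide greater than 95% confidence in detecting issues with a 5% probability of occurrence". For each pain group of 60 it says "this sample will also provide approximately 80% confidence" in "detecting issues with a 5% probability of occurrence in only one group". The term *issues* is not defined there.

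**The concern.** The rule folds two questions into one: whether something happened, and whether the glasses caused it. An event that fails the second question has no stated route into the adverse-event record.

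The causal judgement is made by the wearer, who sees the lens colour, and by providers, who can see it whenever the glasses are worn. Clear lenses may attract less blame for a bad night than tinted ones. If so, equal underlying worsening would appear as unequal event counts. In the other direction, thoracic surgery, opioids and fibromyalgia all offer ready alternative explanations, so a true lens effect could go unrecorded in any arm.

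This matters because good tolerability is one half of the central hypothesis in Purpose of the study, and detection of issues is the main argument for the sample size.

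**Working it through.** **Inputs.** From Data Analysis and Statistical Considerations: 120 in total, 60 per pain group, issue probability 0.05, stated confidence above 95% (total) and about 80% (one group). From the two trial-procedures sections: the recording rule. Assumed, because the documents give no value: a, the share of true issues that someone attributes to the glasses.

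**Step 1: the plan's own figures.** Take detection to mean at least one occurrence, 1-(1-0.05)^n.

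- n=120: 1-0.95^120 = 99.8%. The stated >95% is true but loose.
- n=60: 1-0.95^60 = 95.4%, not about 80%.

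The stated pair is what n=60 (95.4%) and n=30 (78.5%) would give. Requiring at least two occurrences gives 98.4% at 120 and 80.8% at 60, but the text states no such threshold. The section also gives a "15 participant per condition (acute/chronic x green/clear/blue) sample size", although 120/6 = 20. These mismatches are a separate matter that needs its own reconciliation. Below, the stated figures serve only as benchmarks.

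**Step 2: effect of attribution on detection.** If *issues* means recorded adverse events, a true issue is recorded with probability 0.05a, and detection is 1-(1-0.05a)^n.

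| a (assumed) | n=120 | n=60 |
|---|---|---|
| 1 | 99.8% | 95.4% |
| 0.75 | 99.0% | 89.9% |
| 0.50 | 95.2% | 78.1% |
| 0.25 | 77.9% | 53.0% |
| 0.10 | 45.2% | 26.0% |

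Solving for the a at which each stated figure is just met:

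- >95% at n=120: a = (1-0.05^(1/120))/0.05 = 0.49.
- 80% at n=60: a = (1-0.20^(1/60))/0.05 = 0.53.

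The table applies one a to everybody. If attribution differs by lens, the overall figure follows roughly the average. For example, assume 40 participants per lens colour (120/3), with a=0.5 for the 80 tinted wearers and a=0.1 for the 40 clear wearers. Detection is then 1-(0.975^80 × 0.995^40) = 1-(0.132 × 0.818) = 89.2%, with an average a of (80×0.5 + 40×0.1)/120 = 0.37.

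**Step 3: effect on the contrast between arms.** Assume the same true worsening of 20% in every arm. The recorded rate is 0.20 × a.

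| a tinted / a clear (assumed) | Recorded, tinted | Recorded, clear |
|---|---|---|
| 0.50 / 0.50 | 10% | 10% |
| 0.50 / 0.25 | 10% | 5% |
| 0.50 / 0.10 | 10% | 2% |

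At 20 per condition these are 2.0 expected records in a tinted arm against 2.0, 1.0 or 0.4 in the clear arm. With equal attribution there is no spurious difference, only a uniform under-count.

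**The case against.** The strongest reply has five parts.

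1. **The rule is not exclusive.** A reader might infer that an adverse event is recorded only when the glasses are blamed. The sentence gives a sufficient condition and never says that nothing else is recorded. The Data Safety Monitoring Plan it refers to is not supplied and may be broader. This stands: the most one can say is that no other trigger is stated in the text at hand.
2. **Worsening is measured in every arm anyway.** PROMIS-57 covers sleep, mood and pain in clear-lens wearers as in the others, and the phone line carries no causal condition. This stands in large part, so unattributed worsening is not lost altogether. However, no route is stated to generate an event record, no tolerability analysis of these data is described, and the PROMIS-57 domains listed in the acute section include no visual complaints.
3. **Under-counting in the clear arm is unproven.** A reader might also take it as fact. The rule is the same in all arms, and the documents hold no attribution figure. A differential needs unequal attribution, and the clear-versus-tinted asymmetry would not obviously affect green against blue. This stands.
4. **The link to the sample-size section is conditional.** *Issues* is undefined, and the nearest use, in the acute section, already ties the word to the study or the glasses. The plan also states no between-arm test of events. This stands, and is itself a reason to define the term.
5. **Counting everything can be uninformative.** At an assumed 20% background rate, 20 participants give 1-0.8^20 = 98.8% chance of at least one event with no lens effect at all. This stands against restating the detection claim in terms of all-cause worsening. It does not count against recording occurrence and perceived cause separately.

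**Conclusion.** The point holds as a risk built into a stated rule. In both group sections, the one adverse-event trigger given combines worsening with a causal judgement by people who can see the lens colour. Recorded counts would therefore be a weak basis for comparing tolerability between arms, and could miss effects ascribed to the underlying condition or its treatment.

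The size depends wholly on assumed attribution. A reader might conclude that the plan's stated detection confidence collapses under this rule. The figures do not support that: at half attribution they are 95.2% and 78.1%, close to what the plan states, and clear failure needs a lower share, such as 77.9% and 53.0% at one quarter. Even that holds only if *issues* means recorded adverse events.

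The change is worth making, with moderate confidence. It is cheap and has to be made prospectively, since events that were never recorded may not be recoverable.

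**What to change.** - **Recording rule, both group sections.** Record new or worsened sleep, mood, pain or visual complaints in the same way in all three arms, at the contacts already planned, whatever the perceived cause. Hold perceived relation to the glasses as a separate field on the same form.
- **Analysis.** Compare tolerability between arms on all recorded events and on the PROMIS-57 worsening already collected. List attributed events as secondary.
- **Sample-size section.** Define *issues*, and do not turn the detection statement into one about all-cause worsening.
- **Data Safety Monitoring Plan.** If it already records all events, bring the protocol sentence into line with it. No further change to recording is then needed.

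The withdrawal rule that shares this sentence is left to the clinical team.

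Cost: about one sentence in each group section, one form field and a definition. The downside is more non-specific events to log, mainly postoperative ones.

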Opioid Sparing Potential of Light-Induced Analgesia: a Pilot Trial of a Novel, Non-Pharmacological Treatment for Pain

Protocol 1.14 Approved November 10, 2020

Purpose of the study

This offers fascinating potential for use in opioid sparing multimodal analgesia while maintaining pain control, for which there is an urgent need. The green light effect is visually mediated. Further, the green-biased light spectrum involved can be obtained by filtering ambient light. Therefore, if such putative green light analgesia is possible in human populations, it would be inducible simply by using green lensed eyeglasses.

Our long-term goal is to test the efficacy of eyeglasses-based green light therapy as an analgesic adjunct. In particular, we aim to assess green light therapy's potential for broad adoption as an opioid sparing strategy while maintaining pain control. Reductions in opioid exposure are particularly important given links to opioid misuse risk. This aligns with national priorities aiming to identify interventions to prevent opioid misuse and abuse. The objective here, and the next step in pursuit of that goal, is to conduct a pilot trial testing clinical usage of green light therapy as an analgesic adjunct to opioid therapy. Our central hypothesis is that eyeglasses-based green light therapy will be well-tolerated and opioid sparing. The rationale for the proposed study is based on the published findings as described above. Namely, that green light visualization reduces pain responses. We expect that this effect will allow reduced opioid exposures in clinical care.

We will conduct the proposed pilot trial in both acute and chronic pain conditions. Patients scheduled for thoracic surgery with anticipated post-operative opioid treatment (acute surgical pain) and patients with fibromyalgia currently treated with opioids (chronic pain) will be identified, enrolled, and randomized to one of three arms: 1. clear eyeglasses (control), 2. green eyeglasses or 3. blue glasses

Design and Procedures

Trial Procedures – Acute Pain group:

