ensure completion of the questionnaire over the phone with the subjects. The week 2 questionnaire will be completed either over the phone (in the same way as week 1) or on site at the pain clinic. For patients completing the survey on site, the study staff will collect study materials (glasses and diary) at that visit. For patients completing the final study visit (week 2) over the phone, stamped and addressed shipping supplies will be provided to the patient for the return of the study materials (glasses and diary). Study staff will follow up with participants' pain providers to obtain any relevant feedback.

Selection of Subjects

Subjects will be identified through chart review using MaestroCare reports. Inclusion/exclusion criteria for the study will be:

Inclusion

- 1. Scheduled for thoracic surgery for which post-operative opioid PCA is anticipated (Acute Pain group) OR currently treated with opioid therapy for fibromyalgia (Chronic Pain group)
- 2. 18 years of age and older
- 3. Able to wear study eyeglasses for at least 4 hours per day

4. Agree to participate and provide written informed consent and HIPAA authorization Exclusion:

1. Color blindness (patients will be administered a color blindness test online at https://colormax.org/color-blind-test/

Recruitment and Compensation

In identifying and approaching all patients, the study team will coordinate with the primary clinical team. If the eligible patient agrees to hear more about the study, a study team member will attend, explain the study in detail, and obtain written informed consent. For patients who participate in remote enrollment, written electronic consent forms will be provided to the patient via email through REDCap and patients will sign and submit the e-consent. Study staff will then print a copy of the signed e-consent for our records and a copy will be automatically sent to the study participant as well. We will use the Duke hosted REDCap platform for collecting eConsent.

Study Interventions

Patients scheduled for thoracic surgery with anticipated post-operative opioid treatment (acute surgical pain) and patients with fibromyalgia currently treated with opioids (chronic pain) will be identified, enrolled, and randomized to one of three arms: 1. clear eyeglasses (control), 2. green eyeglasses or 3. blue eyeglasses.

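### The stated detection confidences (>95% overall, about 80% in one group) do not fit 120 participants in three arms, and fall short for an issue specific to green lenses

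*Combined protocol and SAP*

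**What the plan says.** The sample size is justified mainly by the chance of observing a problem at least once. Under Data Analysis and Statistical Considerations, the plan says that "a total enrollment of 120 participants will be sufficient to provide greater than 95% confidence in detecting issues with a 5% probability of occurrence". It splits the 120 into 60 acute-pain and 60 chronic-pain participants and adds that "this sample will also provide approximately 80% confidence in detecting issues with a 5% probability of occurrence in only one group".

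It then gives the cell size: "This yields a 15 participant per condition (acute/chronic x green/clear/blue) sample size". On the third arm it says: "Adding the blue glasses group to compare, continues to allow us a similar confidence in detecting issues". No number accompanies that last statement.

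Study Interventions confirms that participants are "randomized to one of three arms: 1. clear eyeglasses (control), 2. green eyeglasses or 3. blue eyeglasses". Purpose of the study sets out what is to be learned: "Our central hypothesis is that eyeglasses-based green light therapy will be well-tolerated and opioid sparing".

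The plan does not give the formula, define an issue, say which participants count as at risk, or say whether one group in the blue-lens sentence means a pain group or a lens arm.

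**The concern.** A clear-lens or blue-lens wearer cannot reveal a problem caused by a green lens. With three arms, only about a third of participants wear green, so the number relevant to green-lens tolerability is much smaller than total enrolment. The two stated percentages also do not belong together at 120 and 60: if 60 people gave about 80%, 120 would give about 96%, but at a 5% rate 60 people already give more than 95%.

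At stake is how an uneventful trial may be read. If no problem appears among green wearers, a reader of the sample-size section could take that as more than 95% assurance against a 5% problem with green lenses, and about 80% within each pain population. The three-arm design provides neither.

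**Working it through.** **Inputs.** Issue probability 5%, total 120, 60 per pain group and 15 per condition are all from Data Analysis and Statistical Considerations. The three arms are from Study Interventions. No allocation ratio is stated; equal allocation is assumed, in line with the single cell size quoted.

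**Formula.** P(at least one event among n at risk) = 1 − (1 − 0.05)^n = 1 − 0.95^n.

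**The plan's own figures.**
- n = 120: 1 − 0.95^120 = 99.8%, which satisfies >95%.
- n = 60: 1 − 0.95^60 = 95.4%, which is not about 80%.
- n = 30: 1 − 0.95^30 = 78.5%, which is about 80%.
- Smallest n for 95%: ln 0.05 / ln 0.95, rounded up, = 59. Smallest n for 80%: ln 0.20 / ln 0.95, rounded up, = 32.

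The pair (>95%, about 80%) is therefore matched by 60 and 30 at risk. Three configurations give those counts:
- all participants in a two-arm trial at 15 per condition (4 × 15 = 60; 30 per pain group);
- green wearers in a two-arm trial of 120 (60; 30 per pain group);
- wearers of either tint in three arms at 15 per condition (4 × 15 = 60; 30 per pain group), which has a total of 90.

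None of these is 120 participants in three arms.

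**Cell size.** Two pain groups × three lenses = 6 conditions. 6 × 15 = 90, whereas 120 / 6 = 20. Both sizes are carried below.

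| At risk | 20 per cell (total 120): overall | 20 per cell: one pain group | 15 per cell (total 90): overall | 15 per cell: one pain group |
|---|---|---|---|---|
| Any participant | n=120: 99.8% | n=60: 95.4% | n=90: 99.0% | n=45: 90.1% |
| Either tint | n=80: 98.3% | n=40: 87.1% | n=60: 95.4% | n=30: 78.5% |
| Green only | n=40: 87.1% | n=20: 64.2% | n=30: 78.5% | n=15: 53.7% |

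At 120, no row gives the stated pair. At either size, no single lens arm reaches 59 and no lens-by-pain cell reaches 32.

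**Effect of a third arm at a fixed total of 120.** Green wearers fall from 60 to 40 overall (95.4% to 87.1%) and from 30 to 20 per pain group (78.5% to 64.2%).

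**Issue rate detectable with 95% confidence**, 1 − 0.05^(1/n), green wearers: 7.2% (n=40) and 13.9% (n=20) at 20 per cell; 9.5% (n=30) and 18.1% (n=15) at 15 per cell.

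**The case against.** The strongest reply is that the >95% sentence is tied to total enrolment and is true as such: 120 people give 99.8%. Issues are undefined, and this is a pilot that also studies usage and compliance. Problems with frame fit, log books, questionnaires or the return of materials can arise in any arm, and counting everyone is then legitimate. This stands, and it limits the point to lens-specific issues.

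Similar confidence also holds on several readings. One lens arm across both pain groups gives 78.5% to 87.1%; either tint within a pain group gives the same range; a whole pain group gives 90.1% to 95.4%. It fails clearly only for a single lens within a single pain group. The sentence carrying the claim repeats one phrase many times, possibly from text extraction, so its intended wording is uncertain.

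A reader might infer that the authors counted clear-lens and blue-lens wearers as at risk. The plan never says so, and counting everyone would have given 95.4%, not about 80%, for a group of 60. A reader might equally infer that the figures survive from a two-arm plan. The reference to adding blue is compatible with that, but either tint at 15 per condition fits the pair too, so the origin cannot be settled.

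Nor are these figures the only numerical support: the same section also cites pilot-trial guidelines of 10 to 15 per condition. No test, stopping rule or go/no-go criterion in the document uses the percentages.

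**Conclusion.** The point holds in a limited form. The two percentages cannot both be derived from one at-risk set in a three-arm trial of 120, and neither applies to a green-lens issue in the corresponding population. Across both pain groups the confidence for such an issue is 79% to 87%, against >95%. Within one pain group it is 54% to 64%, against about 80%, so a true 5% problem would go unseen more than one time in three (100 − 64.2 = 35.8%) and possibly nearly half the time (100 − 53.7 = 46.3%).

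This rests on equal allocation, independent participants with a common 5% probability, and detection meaning at least one occurrence. The width of each range comes only from the unresolved cell size, so 87% and 64% should not be quoted alone.

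It would go too far to call the >95% statement false: it is correct for issues open to any participant. It would also go too far to call similar confidence wrong throughout. The shortfall matters because the tolerability hypothesis is about green lenses, and the plan gives no figure for them.

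**What to change.** First reconcile 120 with 15 per condition, and state the allocation ratio. Then give the formula 1 − 0.95^n, say what an issue is, and name the at-risk set for each figure:

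- **Issues possible in any participant:** 99.8% overall and 95.4% per pain group at 120; or 99.0% and 90.1% at 90.
- **Issues specific to green lenses:** 87% overall and 64% per pain group at 20 per cell; or 79% and 54% at 15 per cell.

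Limit the statement that adding blue leaves confidence similar to the at-risk sets for which it holds, and say that it does not hold for a single lens within one pain group. Quoting the issue rate detectable with 95% confidence beside each green-lens figure would help readers interpret an absence of events.

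The cost is a wording change and less favourable stated figures. Restating the figures needs no extra patients.

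### The sample-size figures contradict each other: 120 over six conditions is 20 each, not 15, and 60 per pain group gives 95.4% detection confidence, not about 80%

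*Combined protocol and SAP*

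**What the plan says.** All of the sizing is in the section Data Analysis and Statistical Considerations of the combined protocol and SAP.

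- Total: "We calculate that a total enrollment of 120 participants will be sufficient to provide greater than 95% confidence" of detecting issues that occur with 5% probability.
- Per pain group: "Divided evenly across Acute Pain and Chronic Pain groups (60 each) this sample will also provide approximately 80% confidence", again for a 5% issue, this time one arising in only one group.
- Per condition: "This yields a 15 participant per condition (acute/chronic x green/clear/blue) sample size".
- After the third lens colour: "Adding the blue glasses group to compare, continues to allow us a similar confidence in detecting issues". No new percentage is given.

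The Study Interventions section confirms that patients in both pain populations are "randomized to one of three arms: 1. clear eyeglasses (control), 2. green eyeglasses or 3. blue eyeglasses". There are therefore 2 × 3 = 6 conditions. The closing paragraph of the sizing section adds that the sample also satisfies pilot-trial guidelines of 10 to 15 per condition.

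**The concern.** The total, the pain-group size, the condition size and the number of conditions cannot all be true together. Separately, the confidence claimed for one pain group does not follow from the size given for that group.

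The condition size is what a randomisation list is built from, and no other allocation figure in the document settles it. A reader who follows the total would plan 20 per condition and stop at 120. A reader who follows the condition size would plan 15 and could stop at 90. The sizing argument itself is split: the detection claim rests on 120, and the appeal to pilot guidelines rests on 15 per condition. The document gives no other numerical support for the sample size.

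**Working it through.** **Inputs**, all from Data Analysis and Statistical Considerations except the number of arms (Study Interventions): total 120; 60 per pain group; 15 per condition; issue probability 0.05; three lens arms in each of two pain groups; stated confidence above 95% overall and about 80% in one group.

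**Step 1: allocation.**
- 120 / 6 = 60 / 3 = 20 per condition, not 15.
- 15 × 6 = 90 in total, and 15 × 3 = 45 per pain group, not 120 and 60.
- Difference in target: 120 − 90 = 30, and 30 / 120 = 25%.

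**Step 2: detection confidence.** The document gives no formula. The usual one for this kind of claim is the probability of at least one event among n people, 1 − (1 − 0.05)^n.

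| n | Corresponds to | 1 − 0.95^n |
|---|---|---|
| 30 | half of 60 | 78.5% |
| 45 | pain group, if 15 per condition | 90.1% |
| 60 | pain group, as stated | 95.4% |
| 90 | total, if 15 per condition | 99.0% |
| 120 | total, as stated | 99.8% |

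The overall claim of more than 95% is true at 120, though well below the actual 99.8%. The 80% claim does not reproduce at 60. Solving 1 − 0.95^n = 0.80 gives n = ln(0.20) / ln(0.95) = 31.4, about half the stated group. For 95%, n = ln(0.05) / ln(0.95) = 58.4, so 59 people suffice.

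**Step 3: which design fits the stated figures?** A total of 60 gives 95.4%, 30 per pain group gives 78.5%, and 60 over four conditions (two pain groups × two lens colours) gives 15 each. All three stated figures therefore fit a 60-participant, two-lens design. This suggests that they were not recalculated when the third colour and the total of 120 came in. That is an inference from the numerical match; the document does not say so.

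**Step 4: other readings.**
- *At least two events required:* n = 60 gives 80.8% and n = 120 gives 98.5%.
- *Issue rate of 2.5%:* n = 60 gives 78.1% and n = 120 gives 95.2%.
- *Group meaning one lens colour pooled over both pain groups:* 30 people at 15 per condition gives 78.5%, but 120 in total means 40 per colour and 87.1%.
- *25% attrition:* 15 / 0.75 = 20, which would make 15 the number of completers.

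The first two match the percentages but leave 15 versus 20 unresolved. The third works only if the total is not 120. The fourth repairs the allocation but not the 80%. None is stated.

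**Step 5: effect on precision.** As an illustration, the 95% confidence interval half-width for a difference in means between two lens arms within a pain group is t(0.975, 2n − 2) × √(2/n), in SD units. It is 0.75 SD at n = 15 and 0.64 SD at n = 20.

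**The case against.** Only one total, 120, is stated outright, and the 60 + 60 split supports it. The figure 90 appears nowhere and is derived from 15 × 6, so 15 may simply be the slip. Every claim of adequacy also survives under either total. Overall confidence is above 95% at both 90 and 120, the confidence within a pain group (90.1% or 95.4%) exceeds the 80% claimed, and both 15 and 20 per condition meet the cited pilot guidelines. Detecting an issue is never defined as one event, and a two-event rule would match both percentages. Finally, the plan does not base its size on between-arm precision, so the interval widths are beside its stated rationale.

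Much of this stands. The 90 is implied, not stated. The 80% error is in the cautious direction and is mild taken alone. The interval widths only illustrate what depends on the cell size. The contradiction itself remains: the text presents 15 as the result of dividing the enrolment over six named conditions, and that division gives 20. A two-event rule is nowhere stated and would not change this.

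**Conclusion.** The concern holds. The stated total and the stated condition size are incompatible by 5 per condition, or 30 participants overall. The confidence for one pain group is misstated by about 15 percentage points (about 80% against 95.4%). The unclear enrolment target is the more important of the two, because the randomisation list and the end of recruitment depend on it.

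The allocation result is plain division and assumes only equal allocation across the three lens arms, since no other ratio is given. The confidence result assumes that detection means at least one occurrence, with independent participants and the stated 5% probability.

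**What to change.** Choose one set of numbers and restate all of them in Data Analysis and Statistical Considerations:

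- **Option A:** 120 total, 60 per pain group, 20 per condition; 99.8% confidence overall and 95.4% within one pain group.
- **Option B:** 90 total, 45 per pain group, 15 per condition; 99.0% overall and 90.1% within one pain group.

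In either case, delete the 80% figure, state that confidence means the probability of observing at least one event, and replace the claim of similar confidence after adding the blue arm with the recalculated values. Build the randomisation list to the chosen cell size. If an attrition allowance or a two-event rule was intended, state it and show the calculation.

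The cost is a wording change, and neither option goes beyond the 120 participants already stated. The choice is still a design decision: Option B reduces the stated enrolment by 25%, and if a list has already been built at 15 per condition, Option A adds 30 people to it.
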